This document is confidential and the property of the Duke University.

List of Abbreviations

6MWT	6 Minute Walk Test
CBC	Complete Blood Count
CMP	Comprehensive Metabolic Panel
CQMP	Clinical Quality Management Program
CRF	Case Report Form
Dx	Diagnose
eCRF	Electronic Case Report Form
FDA	Food and Drug Administration
GCP	Good Clinical Practice
HIPAA	Health Insurance Portability and Accountability Act of 1996
IRB	Institutional Review Board
MRI	Magnetic Resonance Imaging
PFT	Pulmonary Function Test
PHI	Protected Health Information
SOC	Standard of Care
Xe	Xenon

CONFIDENTIAL

This document is confidential and the property of the Duke University.

Study Summary

Title	Characterizing the Long-Term Cardiopulmonary Effects of COVID-19 with Hyperpolarized Xenon and Cardiac MRI
Short Title	COVID Long Haulers
Protocol Number	Pro00107681
Phase	Phase 2
Study Duration	1 year
Study Center(s)	Single site
Objectives	The study will focus on determining whether subjects with persistent and continued dyspnea after COVID infection exhibit unique imaging signatures on Xenon and Cardiac MRI.
Number of Subjects	30 consent and 23 enrolled.
Diagnosis and Main Inclusion Criteria	
Diagnosis of post Coronavirus (COVID-19)
 
Inclusion Criteria
 
 a. Age \geq 18-year-old b. Tested positive for SARS-CoV2 c. Willing and able to give informed consent and adhere to visit/protocol scheduled (consent must be given before any study procedures are performed) 
Exclusion Criteria
 
 a. Prisoners b. Pregnancy, planning pregnancy or lactating c. Conditions that prohibit MRI scanning (metal in eye, claustrophobia, inability to lie supine). d. Medical or psychological conditions which, in the opinion of the investigator, might create undue risk to the subject or interfere with the subject's ability to comply with the protocol requirements
Study Product, Dose, Route, Regimen	Hyperpolarized Xenon (^{129}Xe)
Duration of administration	Open label – Inhalation

CONFIDENTIAL

This document is confidential and the property of the Duke University.

Statistical Methodology	
¹²⁹Xe MRI metrics will include RBC/barrier, barrier/gas, RBC/gas and several spectroscopic indices. Continuous data will be presented using the mean \pm SD if normally distributed and median with 25th and 75th percentiles otherwise. We are fortunate to be able to compare the findings in our images to a database of approximately 30 healthy reference subjects whom we have scanned to date. These subjects have undergone the same ¹²⁹Xe MRI protocol and were recruited with no histories of smoking or cardiopulmonary disease, FEV1>80%, FEV1/FVC>0.70 and DLCO>80%. For subjects to be included in the reference cohort they further had an RBC/barrier ratio \geq0.45 (at TR=15 ms), and image SNR >5, based on the Rose criterion. Comparisons between these groups will use analysis of variance (ANOVA0 methods or Kruskal-Wallis test as appropriate.

-------------------------	---

CONFIDENTIAL

This document is confidential and the property of the Duke University.

1 Introduction

The next phase of the COVID-19 pandemic is likely to see a surge in associated chronic cardiopulmonary disease that will challenge health systems. Recovered patients are presenting with persistent dyspnea at our Duke Pulmonary Post-COVID clinic. Evidence is now mounting that recovered patients have significant residual pulmonary disease, while myocardial injury has also been increasingly reported. To optimally care for these patients, we must comprehensively assess and monitor the changes in cardiopulmonary function and relate them to physiologic and quality of life outcomes. We will deploy cutting edge MRI to fully characterize cardiopulmonary function in enrolled 23 subjects post recovery and 6-9 months later. Cardiac MRI will assess myocardial status and right ventricular function, while hyperpolarized ^{129}Xe MRI will provide 3D assessment of pulmonary ventilation, interstitial barrier integrity and pulmonary vascular hemodynamics. The overall objective outlined in this study is to demonstrate feasibility and value of comprehensive longitudinal imaging characterization of cardiopulmonary structure and function in patients recovered from Covid-19.

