Although the initial presentation of patients with moderate to severe symptoms of COVID19 infections is dominated by respiratory symptoms, 10% go on to develop persistent post-infection symptoms which are thought to have an inflammatory etiology. Evidence suggests that pathologic activation of the inflammasome persists beyond the acute initial presentation that contributes to the persistent disabling symptoms characterized as “long-haul COVID”. For this trial, subjects will be eligible for enrollment if they are outpatients with a history of a laboratory confirmed diagnosis of COVID-19 infection, and after 60 days or longer. We will enroll 13 subjects who continue to have respiratory symptoms (i.e., cough, shortness of breath, dyspnea on exertion). An additional 10 subjects engaged in competitive sports and diagnosed with COVID-19 will also be enrolled. These subjects can be asymptomatic or mildly to moderately. Although rare, cardiac impairment has been documented in <2% of these

CONFIDENTIAL

This document is confidential and the property of the Duke University.

individuals. To our knowledge, XeMRI has not yet been studied in this specific patient subset.

The 6-minute walk test and PFTs will not be used to guide enrollment, but rather will be used in combination with XeMRI/cMRI to assess degree of functional impairment. We will stratify our results based on ethnicity and spirometric abnormalities from those subjects without these findings.

Existing data highlight significant racial and ethnic disparities with historically underserved minority populations (i.e., Black, LatinX) suffering disproportionately higher infection rates and more severe illness compared to Whites. This is reflected by the population enrolled in our RedCAP database and biorepository. As such 30% of subjects enrolled will be required to be from underserved communities.

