2.1 Primary Study Aims

- Aim 1 - Determine the cardiopulmonary structure-function abnormalities that characterize early phase COVID-19 recovery. We anticipate conducting ¹²⁹Xe and cardiac MRI in 13 recovering COVID patients recruited at their clinic visit 60 days' or longer post-discharge from their acute infection. We will recruit patients with new onset persistent and continued dyspnea and to characterize the interstitial, pulmonary vascular and myocardial abnormalities relative to a control population.
- Aim 2 – Characterize the evolution of cardiopulmonary abnormalities over 9 months. Patients will undergo repeat scanning 9 months later to assess changes in all regional parameters acquired from pulmonary and cardiac MRI, directly addressing the possible reversibility of cardiopulmonary limitations arising from “long COVID.”
- Aim 3 – Identify MRI features that predict physiologic outcomes and can alter treatment decisions. Patients will undergo PFTs and quality of life evaluations at 3, 6 and 9 months, as well as detailed clinical histories. These data will be used to understand which baseline imaging features are predictive of long-term quality of life and physiology outcomes as well as those that represent “treatable traits” that can be targeted for therapeutic intervention.

3 Study Design

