^{129}Xe MRI metrics will include RBC/barrier, barrier/gas, RBC/gas, and several spectroscopic indices. Continuous data will be presented using the mean \pm SD if normally distributed and median with 25th and 75th percentiles otherwise. We are fortunate to be able to compare the findings in our images to a database of approximately 30 healthy reference subjects whom we have scanned to date. These subjects have undergone the same ^{129}Xe MRI protocol and were recruited with no histories of smoking or cardiopulmonary disease, FEV1>80%, FEV1/FVC>0.70 and DLCO >80%. For subjects to be included in the reference cohort they further had a ventilation defect percentage \leq 6%, (upper limit of normal VDP (Ebner '19)) as well as RBC/barrier \geq 0.45 (at TR=15 ms), and image SNR>5, based on the Rose criterion. Comparisons between these groups will use analysis of variance (ANOVA) methods or Kruskal-Wallis test as appropriate.

8 Safety and Adverse Events

8.1 *Overview*

As the sponsor of the study, Duke University Medical Center and the Principal Investigator shall be solely responsible for complying, within the required timelines, any safety reporting obligation to competent Health Authorities, IRB and any participating (co or sub) investigators, as defined in applicable laws and regulations. For this protocol, safety data include adverse events and special situations, including pregnancies.

8.2 *Management of Safety data*

This study has been designated as an interventional study. As such, all adverse events, special situations including pregnancies and product quality complaints will be reported as described in this protocol from the time a subject has signed and dated an Informed Consent Form (ICF) until 30 days after the last documented use of the study drugs (i.e., end of study (9 months)).

Adverse Event

An **adverse event** (AE) is any symptom, sign, illness, or experience that develops or worsens in severity during the study. Intercurrent diseases or injuries should be regarded as adverse events. Abnormal results of diagnostic procedures are considered to be adverse events if the abnormality:

CONFIDENTIAL

This document is confidential and the property of the Duke University.

- results in study withdrawal
- is associated with a serious adverse event
- is associated with clinical signs or symptoms
- is associated with Abnormal lab values
- leads to additional treatment or to further diagnostic tests

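### Healthy controls must have RBC/barrier of at least 0.45, but RBC/barrier and its two components are then tested against unfiltered post-COVID subjects; if the rule removed anyone, the test leans toward low post-COVID values

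*Combined protocol and SAP*

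**What the plan says.** The Statistical Methodology entry of the Study Summary describes healthy reference subjects with no history of smoking or cardiopulmonary disease and with FEV1, FEV1/FVC and DLCO above set limits. It then adds imaging conditions: "For subjects to be included in the reference cohort they further had an RBC/barrier ratio" of at least 0.45 (at TR=15 ms), and image SNR above 5. Section 7.2 has the same threshold, introduced by "as well as RBC/barrier", next to a limit on ventilation defect percentage (VDP) that the Study Summary omits.

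Section 7.2 also says that the "MRI metrics will include RBC/barrier, barrier/gas, RBC/gas, and several spectroscopic indices". The controls are "approximately 30 healthy reference subjects whom we have scanned to date". On the test: "Comparisons between these groups will use analysis of variance (ANOVA) methods or Kruskal-Wallis test as appropriate".

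Sections 4.1 and 4.2 set no RBC/barrier limit for post-COVID subjects, and section 2 says that lung-function tests do not guide enrolment. Section 2 describes two kinds of patient: "We will enroll 13 subjects who continue to have respiratory symptoms", and "An additional 10 subjects engaged in competitive sports and diagnosed with COVID-19 will also be enrolled". Aim 1 in section 2.1 is to "characterize the interstitial, pulmonary vascular and myocardial abnormalities relative to a control population".

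The documents do not say how many volunteers failed the 0.45 rule, whether the figure of about 30 is counted before or after it, or whether any analysis without the rule is planned.

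**The concern.** A control group cut off from below on the variable under test no longer represents healthy people on that variable. Its mean can only move up and, for a roughly normal metric, its SD shrinks. Both changes make post-COVID subjects look low on RBC/barrier even if infection has no effect. Low is also the direction that would be read as impaired gas transfer, so a false finding would look plausible.

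The effect does not stop at RBC/barrier. That metric equals RBC/gas divided by barrier/gas, and both are on the list of metrics. Dropping volunteers with a low ratio tends to drop those with low RBC/gas or high barrier/gas, which pushes control RBC/gas up and control barrier/gas down. High barrier uptake, the metric in the sample-size calculation of section 7.1, could be touched through its correlation with RBC/barrier, but the documents do not give that correlation.

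The control comparison in Aim 1 is what is at stake. Aim 2 (change within patients) and Aim 3 (prediction from baseline imaging) do not depend on how controls were chosen.

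**Working it through.** **The plan's own figure.** Section 7.1 concerns high barrier uptake: difference 10, SD 10, 90% power, two-sided. Alpha is not stated; 0.05 is assumed. The normal formula gives n = 2 × (1.960 + 1.282)² × (10/10)² = 21.01, or 22 per group. The t-test gives 22.02, or 23 per group, so the stated 23 reproduces. It says nothing about RBC/barrier, for which the plan gives no mean, SD or power.

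**Inputs.** From the documents: 23 post-COVID subjects, of whom 13 are symptomatic and 10 in competitive sports; about 30 controls; a fixed cut-off for controls only. Assumed: a normal metric, no true difference, 30 controls left after the rule, two-sided 5%, and a share p of eligible volunteers below the cut-off. Since p is unknown, it is shown as a range that starts at zero.

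**Shift and SD of the filtered controls.** Let a be the p quantile of the standard normal and λ = φ(a)/(1 − p). In units of the unfiltered SD, the mean rises by λ and the SD becomes √(1 + aλ − λ²). For p = 5%: a = −1.645, λ = 0.1031/0.95 = 0.109, SD = √(1 − 0.179 − 0.012) = 0.90. The number removed to leave 30 is 30/(1 − p) − 30. The standard error of the group difference is √(1/23 + 1/30) = 0.277 SD.

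| Share removed | Volunteers removed | Rise in control mean (SD) | Control SD ratio | Rise / standard error |
|---|---|---|---|---|
| 0 | 0 | 0 | 1.00 | 0 |
| 2.5% | 0.8 | 0.06 | 0.94 | 0.2 |
| 5% | 1.6 | 0.11 | 0.90 | 0.4 |
| 10% | 3.3 | 0.20 | 0.84 | 0.7 |

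**Type I error.** Simulation with 200,000 replicates: patients from N(0,1), controls from N(0,1) cut off below at a. With p = 0 the tests that were checked come out at about 5%, as they should. KW is Kruskal-Wallis. The 13 vs 30 columns correspond to the patients named in Aim 1; 13/10/30 is the three-group overall test.

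| Share removed | 23 vs 30 ANOVA | 23 vs 30 KW | 13 vs 30 ANOVA | 13 vs 30 KW | 13/10/30 ANOVA | 13/10/30 KW |
|---|---|---|---|---|---|---|
| 2.5% | 5.7% | 5.2% | 5.9% | 5.2% | 6.0% | 5.2% |
| 5% | 6.9% | 6.0% | 7.1% | 5.9% | 7.1% | 5.8% |
| 10% | 11.8% | 9.5% | 11.2% | 8.7% | 11.1% | 8.7% |

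Independent reruns agree to within about 0.3 percentage points. With 23 vs 30, the share of false ANOVA rejections that show post-COVID low rises from about 50% with no removal to 71%, 85% and 96%.

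**Spill-over to the two components.** Assume log RBC/gas and log barrier/gas have equal SDs and correlation ρ. Each then correlates with the log ratio by √((1 − ρ)/2) in absolute value: 0.71 at ρ = 0 and 0.50 at ρ = 0.5. Their shifts are that fraction of λ. With 5% removed this is 0.109 × 0.50 to 0.109 × 0.71, or 0.05 to 0.08 SD; with 10% removed, 0.10 to 0.14 SD. The shift is upward for RBC/gas and downward for barrier/gas.

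**The case against.** - **The harm is not shown.** Nothing in the documents says that a volunteer was removed. This stands. A reader might infer from the rule that the comparison is already biased; the documents do not support that, because the count is absent and may be zero.
- **The effect is probably small.** If 0.45 is a limit of normal, as section 7.2 describes the VDP cut-off (the text does not say so for RBC/barrier), 2.5% to 5% is the natural range and type I error stays at about 7% or below. This stands too. The 10% case is a sensitivity case, not an estimate.
- **The study is exploratory.** Section 4.3 calls it a pilot, section 1 speaks of feasibility and value, no alpha is given and no primary endpoint is named. This lowers the stakes of a 5% error rate, but a built-in lean in one direction misleads a descriptive reader as well.
- **The threshold defines healthy.** That is a legitimate use for a reference range. For a group test it changes the question to post-COVID subjects against volunteers already known to have acceptable RBC/barrier, and the plan does not label it so. Image quality is no defence, since the SNR rule covers it separately.
- **Other differences between the groups remain.** Controls are selected on smoking history and lung function, patients are not, and no matching or adjustment is described. An assumed background difference of 0.1, 0.2 or 0.3 SD would alone give 6.5%, 10.8% or 18.6% rejection. This stands. A reader might infer that readmitting the removed volunteers makes a remaining difference attributable to infection; it does not.

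**Conclusion.** The point holds as a conditional one. The asymmetry is certain: both the Study Summary and section 7.2 select controls on a metric that is then tested against patients who were not so selected. If any otherwise eligible volunteer was removed, the direction is certain too, toward post-COVID low on RBC/barrier, with smaller shifts in RBC/gas and barrier/gas. The size is not known. Under a normal metric, a fixed cut-off, no true difference and 23 vs 30, ANOVA type I error is about 5.7%, 7% and 12% for an assumed 2.5%, 5% and 10% removed, and 5% if none was. The effect is therefore modest unless about 10% were removed.

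Two wider readings are not supported. The sample-size claim in section 7.1 is not undermined by this point, since the link between high barrier uptake and RBC/barrier is not given. Nor would it be right to confine the problem to RBC/barrier, since its two components are tested as well. The change is worth making because it is cheap and the present text does not let a reader rule the bias out.

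**What to change.** In section 7.2 and the Study Summary:

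1. Report how many volunteers who met the history, spirometry, DLCO and image-SNR criteria were removed by the RBC/barrier rule, and whether the figure of about 30 is counted before or after it. If none was removed, say so; no other change is needed.
2. If some were removed and their scans are available, use as comparator for the between-group tests of RBC/barrier, RBC/gas, barrier/gas and high barrier uptake all volunteers scanned with the same protocol who meet the history, lung-function and image-SNR criteria, regardless of RBC/barrier. Keep the filtered cohort for reference ranges and as a sensitivity analysis.
3. If the removed scans are not available, label the comparator as volunteers pre-selected for RBC/barrier of at least 0.45, and treat the RBC/barrier difference as descriptive.
4. State that controls and patients also differ in smoking and lung-function selection, so that a remaining difference is not attributed to COVID-19 alone.

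The VDP limit should read the same in both places; if VDP is itself compared between groups, handle it in the same way for that test.

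Cost: one count from existing records, retrieval of scans already acquired if they were kept (the documents do not say), and a few lines of text. No new subjects or scans are needed. The apparent difference may shrink and the control SD may grow, because volunteers with low values come back in.

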1.1 Background

As patients recover from the SARS-COV-2 virus and present with significant, continued dyspnea and fatigue, there is an urgent need to better characterize their underlying lung and heart function. As the causes for dyspnea are multi-factorial, we must elucidate not only the cardiac and pulmonary causes, but monitor them longitudinally and non-invasively. We now know that the long-term sequelae within the pulmonary system includes diffuse alveolar damage in the setting of ARDS (Bradley '20) as well as significant fibrotic changes (George '20) and pulmonary vascular abnormalities (Ackermann '20). Moreover, recovered patients have been reported to harbor significant myocardial injury on cardiac MRI (CMR) (Puntmann '20). This may be due to: (1) direct myocardial damage from viral infection (Lindner '20) or the effects on the right ventricle from damage to the pulmonary vasculature caused by endothelialitis and thrombosis. Unfortunately, we currently have little understanding of these short- and long-term cardiopulmonary effects in survivors of COVID-19 infection. However, we know they are likely to be multifactorial, with changes to the pulmonary airspaces, interstitium, vasculature and myocardium. Until we can directly and longitudinally measure each of these regional effects on lung and cardiac morphology and function, we will remain blind in our efforts to understand and treat the lingering effects of COVID-19 infection. Here we provide an innovative and non-invasive means to deploy MRI to sensitively and comprehensively characterize the impact of COVID-19 on regional cardiopulmonary function. We will identify the imaging features that can guide the continued care of patients struggling with its enduring effects. We have brought together an interdisciplinary team, ranging from faculty of the Duke pulmonary post-COVID clinic to physicists and engineers who have pioneered hyperpolarized ^{129}Xe pulmonary functional MRI and high-resolution cardiac MRI. This combination of technologies addresses the unmet need by directly, and non-invasively quantifying regional 3D ventilation, alveolar capillary gas exchange, and pulmonary vascular hemodynamics. With the addition of a full cardiac assessment, it can be used to elucidate the causes of dyspnea and monitor progression or resolution of disease non-invasively over time. Our central hypothesis is that noninvasive imaging of the pulmonary airspaces, interstitial membrane and capillary blood volume, combined with cardiac structure/function assessment, provides an unprecedented and

CONFIDENTIAL

This document is confidential and the property of the Duke University.

sensitive means to understand the physiologic evolution of COVID-19 infection, its long-term sequelae, and its treatable traits. This approach to characterizing the aftermath of SARS-CoV2 infection will improve our understanding of the underlying pathology and provide fundamental insights upon which to design future interventions, such as tailoring treatments to specific patterns of cardiopulmonary impairment.

1.2 Investigational Agent

1.2.1 Hyperpolarized ^{129}Xe

^{129}Xe MRI also provides the unique ability to image the diffusive transfer of gas into the alveolar-capillary barrier tissue and red blood cell (RBC) compartments. Like oxygen, ^{129}Xe must traverse the interstitial barrier to reach capillary blood cells (RBCs). Notably ^{129}Xe in barrier tissues and RBCs exhibits a unique frequency shift, allowing it to be separately imaged in each compartment. It has demonstrated sensitivity to gas exchange impairment in pulmonary fibrosis, and pulmonary vascular disease, without ionizing radiation.

1.2.2 Study Dose

Each xenon dose will be limited to a volume less than 25% of subject lung capacity (TLC), as is the case for all protocols currently carried out under IND 109,490.

1.3 Risk and Benefits

1.3.1 Potential Risk

1. Inhalation of hyperpolarized ^{129}Xe may carry some minor risks. Xenon is a general anesthetic when breathed continuously at concentrations greater than 70% for extended periods of time. In the proposed study, Xenon will be delivered in a single breath, with alveolar concentrations below 25%. At these concentrations, subjects may experience transient effects, including dizziness, slight tingling or numbness of the extremities, nausea, smelling of flowers, or a feeling of well-being and euphoria. These effects will wane within 1-2 minutes of exhaling the Xenon and are documented in the consent forms.
2. The risks of participating in the MRI component of the study are considered minimal. MRI is a noninvasive imaging modality that involves no ionizing radiation. At the time of recruitment/consenting and again before the MRI session, all subjects will complete a standard questionnaire to screen for contraindications to MRI imaging (e.g., presence of metal in the eye).
3. There is also the potential risk of loss of confidentiality.
4. Administering HP ^{129}Xe without oxygen - This is necessary to preserve good image quality because O₂ is paramagnetic and depolarizes the HP ^{129}Xe . Therefore, ^{129}Xe is not mixed with O₂ within the dose delivery bag, but only once it is inhaled. Administration of a single anoxic 1-liter breath has been well tolerated by subjects undergoing both ^3He MRI and ^{129}Xe MRI. After a single breath, the residual oxygen in the subject's lungs is sufficient to maintain blood O₂ saturation during the breath-hold. For each subject, their blood-oxygenation will be monitored throughout the time they are in the MRI

CONFIDENTIAL

This document is confidential and the property of the Duke University.

scanner. To reduce risk, a baseline resting oxygen saturation of 90% on supplemental oxygen will be required. Furthermore, supplemental oxygen will be provided during the MRI exam, as indicated.

5. The IV contrast material that is used routinely during the cardiac MRI procedure. However, as with any foreign material in the body, whether food or medicine, there is always the risk of an allergic reaction. Allergic reactions occur uncommonly but may be severe and can result in death. Other specific risks from the contrast agent relate to leaking of the agent at the injection site and side effects or reactions to contrast agents.

